### **4.3 JUSTIFICATION FOR DOSE**

After randomization, participants in both treatment arms will continue to individually dose and titrate NovoLog per the standard of care as judged by the Investigator.

It is recommended that the study drug doses are titrated to achieve a 2 hour postprandial plasma glucose of <180 mg/dL (10 mmol/L) while avoiding hypoglycemia and taking into consideration the content of the meal. Good clinical judgment is to be exercised while titrating the meal-time insulin dose.

In both treatment arms insulin doses of 0.15 U/kg will be administered for PK assessment. This dose is considered sufficient to cover for carbohydrate intake during breakfast without significantly increasing the risk of hypoglycemia (appropriate meal-adjustments and/or potential administration of countermeasures are to be performed by the Investigators to ensure minimization and mitigation of any such risks) and also to provide interpretable insulin profiles over the PK assessment period of 8 hours.

### **4.4 END OF STUDY DEFINITION**

A participant is considered to have completed the study if he/she has completed all phases of the study including the last visit or the last scheduled procedure shown in the Schedule of Activities.

The end of the study is defined as the date of the last visit of the last participant in the study (as scheduled per protocol [PP]).

## 5 STUDY POPULATION

Prospective approval of protocol deviations to recruitment and enrollment criteria, also known as protocol waivers or exemptions, is not permitted.

### 5.1 INCLUSION CRITERIA

Participants are eligible to be included in the study only if all of the following criteria apply:

#### Age

- I 01. Participant must be at least 18 years of age, inclusive, at the time of signing the informed consent.

#### Type of participant and disease characteristics

- I 02. Participants with T1DM.
- I 03. Type 1 diabetes diagnosed at least 12 months before screening.
- I 04. Participants on continuous insulin treatment for at least 12 months prior to screening.
- I 05. Participants exclusively on a multiple ( $\geq 3$ ) daily injection insulin analogue regimen using:
- a NovoLog as mealtime insulin for at least 12 weeks prior to screening.

AND

- b Insulin glargine (100 U/mL) as basal insulin for at least 12 weeks prior to screening.

**Note:** Participants not meeting this criterion may also qualify, provided that they complete the run-in period during which NovoLog and Lantus will be administered so that, at the time of randomization, the participants have been on NovoLog and insulin glargine (100 U/mL) for at least 12 weeks (including any potential pre-screening administration).

**Note:** Off-label twice-daily (BID) dosing of insulin glargine is not permitted during the study and any participant administering Lantus BID prior to the study must be switched to once-daily (QD) dosing after signing the Informed Consent for the study (daily time of administration to be agreed between the participant and the study doctor).

- I 06. HbA1c less or equal to 10% (85.79 mmol/mol) at screening.

**Note:** The Sponsor will monitor baseline HbA1c levels and may limit enrollment of participants with HbA1c values  $< 7.0\%$  at a certain point during the conduct of the study to ensure an acceptably high average HbA1c for the study. Sites will be appropriately and timely informed if and when such a decision has been reached.

## Weight

I 07. Body mass index  $\leq 35$  kg/m^2 at screening.

## Sex

I 08. Male or Female.

- Female participants: A female participant is eligible to participate if she is not pregnant (see Appendix 4 [Section 10.4]), not breastfeeding, and at least one of the following conditions applies:
  - Not a WOCBP as defined in Appendix 4 (Section 10.4),  
OR
  - A WOCBP who agrees to follow the contraceptive guidance in Appendix 4 (Section 10.4) during the intervention period and for at least 5 weeks after the last dose of study intervention.

## Informed Consent

I 09. Capable of giving signed informed consent as described in Appendix 1 (Section 10.1.3) which includes compliance with the requirements and restrictions listed in the informed consent form (ICF) and in this protocol.

## 5.2 EXCLUSION CRITERIA

Participants are excluded from the study if any of the following criteria apply:

### Medical conditions

- E 01. Any clinically significant abnormality identified either in medical history, during physical examination, laboratory tests, or vital signs at the time of screening or any AE during screening period which, in the judgment of the Investigator, would preclude safe completion of the study or constrains PK, immunogenicity, safety, or efficacy assessments.
- E 02. Pancreatectomy and/or islet cell transplantation.
- E 03. Severe renal disease defined as estimated glomerular filtration rate (GFR) (modification of diet in renal disease [MDRD] formula)  $< 30$  mL/min/1.73/m^2 or on renal replacement treatment.
- E 04. Known presence of factors that interfere with the HbA1c measurement (eg, specific hemoglobin variants, hemolytic anemia) compromising the reliability of HbA1c assessment or medical conditions that affect interpretation of HbA1c results (eg, blood transfusion or severe blood loss in the last 3 months prior to randomization, any condition that shortens erythrocyte survival).

E 05. Laboratory findings at screening:

- Alanine aminotransferase (ALT) or aspartate aminotransferase (AST) >3 times upper limit of the normal (ULN). Or
- Total bilirubin >1.5 times ULN (except in case of documented Gilbert's syndrome).

E 06. History of severe hypoglycemia requiring emergency room admission or hospitalization within 3 months prior to screening.

E 07. Hospitalization for recurrent diabetic ketoacidosis within 3 months prior to screening.

E 08. Retinopathy or maculopathy with one of the following treatments, either recent (within 3 months of screening) or planned: intravitreal injections or laser or vitrectomy surgery.

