### 1.3.2 SoA for participants with run-in

This SoA is valid for participants who have not been on NovoLog and insulin glargine (100 U/mL) for at least 12 weeks before the screening visit.

	Screening	Run-in		Open-label Treatment Period					Follow-up	Notes
Week	-14	-12	-1 	0 (D1)	4	8	12	16 EOT	16 + 1 day 	Visit Windows: Visit 1: 4 to 14 days before Visit RI; Visit RI: up to 87 days before Visit 3 Visit 2: may be adjusted as appropriate to accommodate Visit 3 date; Visits 4 to 6: ±2 days; Visit 7: ±3 days; Visit 8: +2 days.
Day	-98	-84	-7	1	28	56	84	112	113	
Visit	1	RI	2	3	4	5	6	7	8	
Informed consent	X									Prior to any study-related procedures being performed.
Inclusion and exclusion criteria	X	X	X	X						Recheck eligibility before randomization.
Demography, medical/surgical/medication history, diabetes history	X									Including alcohol, drug abuse, and smoking history.
Physical examination	X							X		See Section 8.2.1
Blood pressure and heart rate	X			X				X		See Section 8.2.2
Body weight	X			X				X		
Height and BMI	X									
Dispensation of study glucometer/supplies and diary	X									Supplies may be re-dispensed any time during the study, as necessary.
Training and retraining on glucometer use, SMPG, hypoglycemia awareness and management, diary use and IMP/NIMP dosage self-adjustment	X	X	X	X	X	X	X			Site will provide training at Visits 1, RI, and 3; regular refresher instructions will be provided at noted visit or as necessary throughout the study.

	Screening	Run-in		Open-label Treatment Period					Follow-up	Notes
Week	-14	-12	-1 ☎	0 (D1)	4	8	12	16 EOT	16 + 1 day ☎	Visit Windows: Visit 1: 4 to 14 days before Visit RI; Visit RI: up to 87 days before Visit 3 Visit 2: may be adjusted as appropriate to accommodate Visit 3 date; Visits 4 to 6: ±2 days; Visit 7: ±3 days; Visit 8: +2 days.
Day	-98	-84	-7	1	28	56	84	112	113	
Visit	1	RI	2	3	4	5	6	7	8	
Diet and lifestyle counseling	X	X	X	X	X	X	X	X	X	As per current practice
IRT contact	X			X	X	X	X	X	X	Additional IRT contact (eg, to request additional IMP/NIMP) is permitted, as necessary

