**Prior/concomitant therapy**

E 09. Likelihood to require treatment prohibited by the protocol during the study.

E 10. Use of glucose lowering treatments other than the multiple dose injection (MDI) and basal insulin regimen, as described in I 05 (including use of insulin pump therapy), within 12 weeks prior to screening.

E 11. Participants having received systemic glucocorticoids for one week or more within 3 months prior to screening (topical, nasal spray, inhaled or intra-articular applications are allowed).

E 12. Participants having received systemic immunosuppressive agents within 6 month prior to screening (please refer to E 11 for restrictions related to glucocorticoids).

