**Other exclusions**

E 14. Any contraindication to use of insulin glargine and/or NovoLog as defined in the national product labels.

E 15. Hypersensitivity to any of the study treatments, or components thereof.

E 16. History of drug or alcohol abuse within 6 months prior to screening.

- E 17. Night shift workers.
- E 18. Participant is an employee of the Sponsor, or is the Investigator or any Subinvestigator, research assistant, pharmacist, study coordinator, other staff or relative thereof directly involved in the conduct of the protocol.

**Additional criteria at the end of the screening period (for participants who do not undergo run-in) or at the end of the run-in period (for participants who undergo run-in)**

- E 19. Participants unwilling or unable to comply with study procedures as outlined in the protocol.
- E 20. Participants who withdraw consent during the screening period (starting from signed ICF) or the run-in period.
- E 21. Participants who used glucose lowering treatments other than Novolog and insulin glargine (100 U/mL) (including use of insulin pump therapy) during the screening period (for participants who do not undergo run-in) or run-in period (if applicable).

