### Note:

- Short term therapy (up to 10 days maximum) with either basal insulin or short acting insulin that may occur due to acute illness or surgery is allowed after the first administration of IMP but not during the screening and run-in periods,
  - Any antidiabetic medication, according to local standard of care, per the Investigator's judgment can be used after definitive premature IMP discontinuation,
  - Administration of additional meal-time insulin during the 8-hour PK period, according to the Investigator's judgement is also permitted. Due to considerations related to the sensitivity of the insulin aspart PK assay, human insulin must be used during this timeframe. Alternatively, administration of insulin lispro at low doses, according to the Investigator's judgement, is also permitted.
- Systemic glucocorticoids for more than 10 days (topical, nasal spray, inhaled or intra-articular applications are allowed).
  - Immunosuppressive agents.
  - Any other investigational product (ie, participation in another clinical trial).

Concomitant medications should be kept to an absolute minimum and doses should be kept stable unless safety concerns indicate changes of dose.

There is no rescue therapy defined in this study. Hypoglycemia will be managed as appropriate, by administering countermeasures, according to the clinical judgement of the Investigator.

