## 10.5 APPENDIX 5: LIVER SAFETY: SUGGESTED ACTIONS AND FOLLOW-UP ASSESSMENTS

### INCREASE IN ALT

**In ANY CASE, FOLLOW** the instructions listed in the box below:

1. **INFORM** the Site Monitor who will forward the information to the Study Manager
2. **INVESTIGATE** specifically for malaise with or without loss of consciousness, dizziness, and/or hypotension and/or episode of arrhythmia in the previous 72 hours; rule out muscular injury
3. **PERFORM** the following tests:
  - LFTs: AST, ALT, alkaline phosphatase, total and conjugated bilirubin and prothrombin time / INR
  - CPK, serum creatinine, complete blood count
  - Anti-HAV IgM, anti-HBc IgM (HBV-DNA if clinically indicated), anti-HCV and HCV RNA, anti-CMV IgM and anti-HEV IgM antibodies
  - Depending on the clinical context, check for recent infection with EBV, herpes viruses, and toxoplasma
  - Hepatobiliary ultrasonography (or other imaging investigations if needed)
4. **CONSIDER** Auto-antibodies: antinuclear, anti-DNA, anti-smooth muscle, anti-LKM
5. **CONSIDER** consulting with hepatologist
6. **CONSIDER** patient hospitalisation if INR>2 (or PT<50%) and/or central nervous system disturbances suggesting hepatic encephalopathy
7. **MONITOR LFTs after discontinuation of IMP:**
  - As closely as possible (or every 48 hours) until stabilization, then every 2 weeks until return to normal/baseline or clinical resolution.
8. **FREEZE** serum sample (5ml x 2)
9. **In case of SUSPICION of GILBERT Syndrome**, a DNA diagnostic test should be done

\*If unable to retest in 72 hours, use original lab results to decide on further reporting/monitoring/discontinuation.

Note:

- “Baseline” refers to ALT sampled at baseline visit; or if baseline value unavailable, to the latest ALT sampled before the baseline visit. The algorithm does not apply to the instances of increase in ALT during screening.
- See [Section 10.3](#) for guidance on safety reporting.
- Normalization is defined as ≤ULN or baseline value, if baseline value is >ULN.

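### Exclusion criteria E 01 (adverse-event part), E 05 and E 06, and partly E 07, stop at screening, so events in the run-in of up to 12 weeks before randomization fall outside them

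*Protocol*

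**What the plan says.** Protocol Section 5.2 ties these criteria to screening:

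- E 01 covers abnormalities found at screening and "any AE during screening period which, in the judgment of the Investigator, would preclude safe completion of the study".
- E 05 applies to "Laboratory findings at screening".
- E 06 excludes for "History of severe hypoglycemia requiring emergency room admission or hospitalization within 3 months prior to screening".
- E 07 applies the same 3-month look-back from screening to hospitalization for recurrent ketoacidosis.

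Other criteria in the same section do reach past screening. The blood-loss example in E 04 counts back from randomization. A separate list applies at the end of screening or, for run-in participants, at the end of run-in; it contains only E 19 (compliance), E 20 (consent) and E 21 (other glucose-lowering treatment). E 20 names the two periods separately: "Participants who withdraw consent during the screening period (starting from signed ICF) or the run-in period".

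The schedule for run-in participants (Section 1.3.2) sets the windows as "Visit 1: 4 to 14 days before Visit RI; Visit RI: up to 87 days before Visit 3". For direct entry (Section 1.3.1), Visit 1 is 7 to 17 days before Visit 3. The run-in schedule rechecks eligibility at Visits RI, 2 and 3. It also draws hematology and chemistry at Visit 3, which the direct-entry schedule does not.

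**The concern.** Participants enter run-in already judged eligible on their screening evaluations, and many are moving to an insulin regimen on which they were not established. Severe hypoglycemia, an intercurrent illness or an abnormal liver test is plausible in those weeks. A criterion fixed to screening gives the same answer at every recheck, however often eligibility is reviewed.

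The two entry routes therefore meet different standards at the same randomization visit. Someone hospitalized for severe hypoglycemia three weeks before Visit 1 is excluded by E 06. Someone hospitalized for it three weeks before Visit 3, during run-in, is not, and could be randomized and later receive the fixed-dose PK injection.

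Reporting is affected too. SAP Section 2.2.1 counts randomization of an ineligible patient as an irregularity. An event that no criterion covers does not make the patient ineligible, so it would not be counted there.

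**Working it through.** **1. Reproduce the plan's own durations, to confirm how its windows are read.**

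- With run-in: 14 + 84 + 112 + 1 = 211 days = 30.1 weeks. With the 3-day extension, 214 days = 30.6 weeks. The plan states less than 31 weeks.
- Direct entry: 14 + 112 + 1 = 127 days = 18.1 weeks. With the 3-day extension, 130 days = 18.6 weeks. The plan states less than 19 weeks.

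Both figures reproduce.

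**2. Gap G from Visit 1 to randomization (Visit 3).**

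- Direct entry: G = 7 to 17 days (Section 1.3.1).
- Run-in: G = screening (4 to 14 days) + run-in length (Section 1.3.2).
- Full run-in of 84 to 87 days: G = 4 + 84 = 88 to 14 + 87 = 101 days.

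**3. How much of the 3 months before randomization the look-back in E 06 and E 07 reaches.** Take 3 months as 91 days. Days covered = max(0, 91 − G).

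| Route | G (days) | Covered, of the last 91 days |
|---|---|---|
| Direct entry | 7–17 | 74–84 |
| 4-week run-in | 32–42 | 49–59 |
| 8-week run-in | 60–70 | 21–31 |
| Full run-in | 88–101 | 0–3 |

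**4. What reaches a run-in event, criterion by criterion.**

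| Criterion | Anchor in Section 5.2 | What else applies in run-in |
|---|---|---|
| E 01, adverse events | Screening period | Discretionary withdrawal (7.1.1, 7.2) |
| E 05, liver tests | Screening result | Chemistry is drawn at Visit 3, but no criterion refers to it |
| E 06, severe hypoglycemia | 3 months before screening | Discretionary withdrawal; E 21 only if another insulin is used |
| E 07, ketoacidosis | 3 months before screening | E 21 if another insulin is used; otherwise discretionary withdrawal |

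For direct entry, the screening period runs up to randomization, so the adverse-event part of E 01 also covers the 7 to 17 days that the look-back misses. For run-in participants that part of E 01 stops at Visit RI, leaving up to 87 days outside it.

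**The case against.** The case against has several parts, and some of them stand.

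- **Eligibility is rechecked, and Section 5.4 counts run-in eligibility failures as screen failures.** This shows the intent to stop unsuitable participants before randomization. It does not change the wording being rechecked.
- **The investigator can act anyway.** Section 7.1.1 says a participant should stop IMP and NIMP if, in the investigator's opinion, continuing would be detrimental. Run-in NovoLog and Lantus are NIMPs. Section 7.2 allows withdrawal at discretion. E 01 is itself a matter of judgment, so extending it adds clarity more than compulsion. E 05 and E 06 are different: before screening they exclude without discretion.
- **E 07 is partly covered.** Section 6.5 does not allow short-term use of other insulin for acute illness during run-in, and E 21 excludes for other glucose-lowering treatment. A ketoacidosis admission treated with another insulin would exclude.

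A reader might infer three further gaps that the documents do not support.

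- **E 08 (retinopathy treatment).** It covers treatment within 3 months of screening, without limiting that to the time before, and also planned treatment. It already reaches into run-in.
- **Glucocorticoids.** E 11 excludes "Participants having received systemic glucocorticoids for one week or more within 3 months prior to screening", while Section 6.5 prohibits "Systemic glucocorticoids for more than 10 days (topical, nasal spray, inhaled or intra-articular applications are allowed". The durations differ, but the Section 6.5 limit applies during direct-entry screening as well as run-in. The mismatch exists on both routes and is not a product of the run-in.
- **A high Visit 3 ALT masking later liver signals.** Appendix 5 says that baseline "refers to ALT sampled at baseline visit; or if baseline value unavailable, to the latest ALT sampled before the baseline visit". The decision tree that uses this baseline is not visible in the available text, so no harm can be shown from it. ALT above 3 times the upper limit is also an event of special interest, reportable within 24 hours (Section 8.3).

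E 03 (severe renal disease) has no time anchor. A Visit 3 estimate of renal function could be applied under it at recheck, although the protocol does not say so.

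**Conclusion.** The point holds for E 01 (adverse-event part), E 05 and E 06, and in part for E 07. It rests on reading screening and run-in as separate periods, which is how the protocol uses the terms, and on taking 3 months as about 91 days.

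For a full run-in, the look-back covers 0 to 3 of the last 91 days before randomization, against 74 to 84 for direct entry. It would be wrong to infer that every run-in participant loses the whole look-back. Run-in is shortened by earlier use of the same insulins, and a 4-week run-in keeps 49 to 59 days. The documents give neither the number of run-in participants nor the event rates, so the number affected cannot be estimated.

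It would also be wrong to infer a biased primary result. These events precede randomization and such participants can enter either arm. The sample-size inputs (73 evaluable per arm, log-scale SD 0.35, true ratio 0.95 to 1.05) do not depend on these criteria. What is at stake is participant safety and consistent eligibility across the two entry routes. That makes this an inexpensive improvement rather than a threat to the trial's conclusion.

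**What to change.** Reconcile Section 5.2 with the run-in design, including Sections 5.4 and 6.5 and the run-in schedule:

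- State that the adverse-event part of E 01 covers the screening period or the run-in period.
- State that E 05, E 06 and E 07 are assessed up to randomization for run-in participants, and list them among the end-of-run-in checks. Their thresholds need not change.
- Say whether and how the chemistry already scheduled at Visit 3, before randomization, is used for eligibility.
- Leave E 08 as it is.
- Reconcile the glucocorticoid durations in E 11 and Section 6.5, as a separate matter that concerns both routes. No duration is proposed here.

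The cost is amendment wording and a few extra run-in failures. No additional visit or blood draw is required, and sample size and power stay as planned.

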**Prior/concomitant therapy**

E 09. Likelihood to require treatment prohibited by the protocol during the study.

E 10. Use of glucose lowering treatments other than the multiple dose injection (MDI) and basal insulin regimen, as described in I 05 (including use of insulin pump therapy), within 12 weeks prior to screening.

E 11. Participants having received systemic glucocorticoids for one week or more within 3 months prior to screening (topical, nasal spray, inhaled or intra-articular applications are allowed).

E 12. Participants having received systemic immunosuppressive agents within 6 month prior to screening (please refer to E 11 for restrictions related to glucocorticoids).

**Prior/concurrent clinical study experience**

E 13. Exposure to any investigational drugs in the last 4 weeks or 5 half-lives, whichever is longer, prior to screening or concomitant enrollment in any other clinical study involving an investigational study treatment. Patients having received SAR341402 at any time prior to screening are not permitted to participate in the study.

**Diagnostic assessments**

Not applicable.

**Other exclusions**

E 14. Any contraindication to use of insulin glargine and/or NovoLog as defined in the national product labels.

E 15. Hypersensitivity to any of the study treatments, or components thereof.

E 16. History of drug or alcohol abuse within 6 months prior to screening.

- E 17. Night shift workers.
- E 18. Participant is an employee of the Sponsor, or is the Investigator or any Subinvestigator, research assistant, pharmacist, study coordinator, other staff or relative thereof directly involved in the conduct of the protocol.

**Additional criteria at the end of the screening period (for participants who do not undergo run-in) or at the end of the run-in period (for participants who undergo run-in)**

- E 19. Participants unwilling or unable to comply with study procedures as outlined in the protocol.
- E 20. Participants who withdraw consent during the screening period (starting from signed ICF) or the run-in period.
- E 21. Participants who used glucose lowering treatments other than Novolog and insulin glargine (100 U/mL) (including use of insulin pump therapy) during the screening period (for participants who do not undergo run-in) or run-in period (if applicable).

